10.3.2.2 Analysis of the secondary variables

10.3.2.2.1 Menstrual blood loss

This section was changed in Amendment 1, see Section 15.1.1.10.

Menstrual blood loss (MBL) at beginning of year 6, end of year 6, end of year 7, and end of year 8 of Mirena treatment will be presented by descriptive statistics. Furthermore, change from baseline (=beginning of year 6) will be presented.

The basis for this analysis is the data on MBL assessed by the alkaline hematin method (see section 9.4.2). If a woman has documented in the eDiary (see section 9.7.1) that no bleeding occurred during one of the 30-day time periods considered for collection of sanitary products, the MBL will be assumed to be zero in that time period. The handling of partial or missing data (i.e. data on sanitary products and/or bleeding intensities) and detailed imputation rules will be described in the statistical analysis plan.

This analysis will be conducted in the FAS in the HMB subgroup, i.e. women who had Mirena inserted for both contraception and HMB.

CCI

CCI [REDACTED]

[REDACTED]

[REDACTED]

[REDACTED]

- [REDACTED]
- [REDACTED]

[REDACTED]

[REDACTED]

- [REDACTED]
- [REDACTED]

[REDACTED]

[REDACTED]

- [REDACTED]
- [REDACTED]
- [REDACTED]

[REDACTED]

[REDACTED]

- [REDACTED]
- [REDACTED]
- [REDACTED]

CCI [REDACTED]

- [REDACTED]
- [REDACTED]
- [REDACTED]
- [REDACTED]

[REDACTED]

- [REDACTED]
- [REDACTED]
- [REDACTED]
- [REDACTED]

Success will be concluded regarding this endpoint if less than 20% of the women in the HMB subgroup have a clinical change in bleeding profile regarding HMB (according to the definition above) and the upper limit of the corresponding 95% Clopper-Pearson confidence interval is equal to or less than 35%.

This analysis will be conducted in the FAS in the HMB subgroup, i.e. women who had Mirena inserted for both contraception and HMB.

10.3.2.3 Analysis of safety variables

This section was changed in Amendment 1, see Section 15.1.1.15 and 15.1.1.26.

All safety variables will be analyzed based on the SAF.

The main safety variable is the incidence of treatment-emergent adverse events (both serious and non-serious). Treatment-emergent AEs are defined as any AEs occurring during the 'extension treatment period' starting at Day 1 of Year 6 of Mirena use.

10.3.2.3.1 Adverse events

All AEs will be classified using MedDRA. The latest available version at the time of coding will be used. The results will be summarized, at a minimum, on the level of system organ class (SOC) and preferred term (PT). Data will also be summarized according to intensity and investigator's causality assessment.

10.3.2.3.2 Bleeding pattern

This section was changed in Amendment 1, see Sections 15.1.1.10, 15.1.1.19, and 15.1.1.26.

Bleeding diary data during the ‘extension treatment period’ starting at Day 1 of Year 6 of Mirena use will be analyzed according to the sponsor’s Best Practice Document entitled “Recording and evaluation of bleeding data”. Bleeding diary data prior to the ‘extension treatment period’ will not be included in the analyses. The handling of partial or missing data and detailed imputation rules will be described in the statistical analysis plan.

Bleeding intensity will be recorded by the subject on a daily basis using the categories presented in Table 9–3 in section 9.6.3.12.

In addition to absolute number of bleeding days, bleeding/spotting episodes will also be assessed according to the sponsor’s Bleeding Intensity Codes and the World Health Organization (WHO) definitions as provided in Table 10–2.

Table 10–2 Bleeding Intensity Codes and WHO Definitions for Bleeding Intensity – amended

Bleeding Intensity Codes	WHO Definitions	
2 - 5	Bleeding/spotting episode:	Day(s) with bleeding/spotting preceded and followed by at least 2 bleeding-free days.
2	Spotting-only episode:	Day(s) with spotting preceded and followed by at least 2 bleeding-free days.
1	Bleeding/spotting-free interval:	At least 2 days without bleeding/spotting preceded and followed by at least 1 bleeding/spotting day.

In addition to the WHO definitions, a **bleeding episode** is defined as day(s) with bleeding/spotting of which at least one day is of intensity 3 or higher, preceded and followed by at least 2 bleeding-free days.

In the following example (Table 10–3) of an assessment of bleeding episodes the above definitions are applied to determine whether the event consisted of a **single bleeding episode** or **multiple bleeding episodes**. In Table 10–3, each recorded bleeding event consists of 5 bleeding days. However, as shown and described, the pattern of bleeding determines whether the 5 days are considered as one or two bleeding episodes.

Based on daily data obtained from the electronic diary, the bleeding pattern will be reported using reference periods of 28 and 90 days. The first 28-day and 90-day reference period, respectively, will start at Day 1 of Year 6 of Mirena use. For each subject and for each period, the number of bleeding/spotting days and bleeding/spotting episodes will be calculated. If the bleeding intensity is recorded as light, normal or heavy, this will be considered as ‘bleeding’.

For each subject and for each 28-day reference period and each 90-day reference period, the

following bleeding indices will be calculated:

- number of subjects with at least one bleeding/spotting day
- number of subjects with at least one bleeding (excluding spotting) day
- number of bleeding/spotting days
- number of bleeding days (excluding spotting)
- number of spotting only days
- number (mean length, maximal length, and range of length) of bleeding/spotting episodes
- number (mean length, maximal length, and range of length) of spotting only episodes (will only be calculated for those subjects who have at least 1 spotting-only episode)

Table 10–3 Example of an Assessment of Bleeding Episodes

A				1	2	3	4	5							one episode of 5 days
B				1	2			1	2	3					two episodes; one of 2 days, one of 3 days
C				1	2	3	4	5	6	7	8				one episode of 8 days
D				1	2	3			1	2	3				two episodes of 3 days each

Denotes bleeding Denotes no bleeding

Scenario A: one bleeding episode of 5 consecutive days; there is no bleeding/spotting-free interval

Scenario B: two bleeding episodes; there is a 2-day bleeding/spotting-free interval between the 2-day episode and the 3-day episode

Scenario C: one bleeding episode; although there are bleeding-free days between bleeding days, the definition of a bleeding/spotting-free interval requires 2 consecutive days

Scenario D: two bleeding episodes; although there is one bleeding-free day in the first 3-day episode, the definition of a bleeding/spotting-free interval requires 2 consecutive days. There is the required 2-day bleeding/spotting-free interval between the two 3-day episodes.

Furthermore, for each 90-day reference period the following bleeding indices were provided according to the WHO criteria:

- number of subjects with amenorrhea, defined as no bleeding/spotting throughout the reference period
- number of subjects with prolonged bleeding, defined as subjects with bleeding/spotting episodes lasting more than 14 days
- number of subjects with frequent bleeding, defined as subjects with more than 5 bleeding/spotting episodes
- number of subjects with infrequent bleeding, defined as subjects with 1 or 2 bleeding/spotting episodes
- number of subjects with irregular bleeding, defined as subjects with 3 to 5 bleeding/spotting episodes and less than 3 bleeding/spotting-free intervals of 14 days or more.
- number of subjects with normal bleeding / none of the above.

10.3.2.3.3 Other safety variables

All other safety variables will be analyzed descriptively using summary statistics or frequency tables as appropriate.

10.3.2.4 Other variables

10.3.2.4.1 Pharmacokinetic parameters

Pharmacokinetic data collected during the study will be analyzed descriptively.

Population PK analysis will be performed as described in a separate M&S Analysis Plan and reported in a separate M&S Report.

10.3.2.4.2 Residual LNG content

Residual LNG content will be analyzed descriptively.

10.3.2.4.3 Discontinuation rate

The discontinuation rate will be provided, calculated from the number of subjects with an expulsion, plus those who have Mirena removed due to partial expulsion or perforation, plus those who discontinue study treatment for other reasons. The Kaplan-Meier estimate will be used.

10.3.2.4.4 Subject satisfaction

The subject's satisfaction with the Mirena on a 5-point scale (very satisfied, somewhat satisfied, neither satisfied or dissatisfied, dissatisfied, very dissatisfied) will be summarized descriptively.

10.3.2.4.5 Mirena removal: ease and pain

The ease of Mirena removal (easy, slightly difficult, very difficult) will be summarized descriptively.

The pain during the removal (none, mild, moderate, severe) will be summarized descriptively.

10.4 Determination of sample size

The sample size calculation is not based on statistical considerations. It is targeted to have 200 women completing the 8th year of treatment with Mirena. With an estimated dropout rate of 15%, the total number of women to be enrolled into the study treatment phase would be 350.

In order to account for women excluded from the primary analysis due to age restrictions (i.e. women 34 years of age at baseline or older will not be included in the primary analysis set 'PAS year 8' for the final analysis after 8 years)², the total number of women to be enrolled into the study treatment phase is 360.

² It is assumed about 90% of women enrolled will be 18 to 32 years of age at screening, i.e. 10% of women will be 33 to 35 years old and accordingly less will be 34 to 35 years old.

Sample size characteristics regarding the analysis of the Pearl index:

This sample size will lead to an expected exposure (years 6 to 8 combined) of 832 women years (WY). Assuming a true Pearl index of 0.2,

- the upper limit of the 95% confidence interval for the PI (years 6-8) will not exceed 1 with a probability of 76%,
- the difference between the point estimate and the upper limit of the 95% confidence interval will not exceed 1 with a probability >99.9%.

Assuming a slightly higher true Pearl index of 0.3,

- the upper limit of the 95% confidence interval for the PI (years 6-8) will not exceed 1 with a probability of 55%,
- the difference between the point estimate and the upper limit of the 95% confidence interval will not exceed 1 with a probability >99.9%.

CCI

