The target for the total number of women to be included in the extended treatment period is 360 women (200 women to complete study treatment). To evaluate the effect of extended Mirena use on HMB, it is targeted that 10% of the women to be treated (i.e. 36 women out of 360) should have Mirena prescribed for the treatment of HMB in addition to contraception. Please note, subjects who have Mirena prescribed for contraception and heavy menstrual bleeding will have to consent to the HMB subgroup procedures.

The study will consist of a screening, treatment, and a follow-up period. Screening can be started when the subject has had the Mirena in place for 4 years and 6 months. Screening activities should be completed within 60 days after signed informed consent to allow enough time for the evaluation of the subjects' eligibility to the study. Baseline visit (Visit 2) will be scheduled to take place 0 to 14 days before the end of Year 5 of Mirena use; and this is the start of the treatment period. Treatment period is defined as the 3-year period following the Baseline visit, i.e. years 6, 7 and 8 of extended use of Mirena.

This section was changed in Amendment 1, see Section 15.1.1.1. An analysis of the efficacy and safety data will be conducted after all subjects have either completed 6 years of treatment (i.e. completed 1 year in the study), or prematurely terminated their study participation before this time point. Another analysis of the efficacy and safety data will be conducted after all subjects have either completed 7 years of treatment (i.e. completed 2 years in the study), or prematurely terminated their study participation before this time point.

Final analysis will be done after all subjects have either completed 8 years of treatment or prematurely terminated their study participation.

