9.6.3.8 Presence of Mirena removal threads

This section was changed in Amendment 1, see Section 15.1.1.22.

The presence of the removal threads will be checked at each study visit and recorded in the eCRF.

The investigator will perform pelvic examinations at each study visit to verify the presence of the Mirena removal threads in the appropriate location in the cervical os. If the presence of the removal threads cannot be verified, transvaginal ultrasound (TVUS) is to be performed to verify that the Mirena is in the appropriate intrauterine location and to exclude expulsion or perforation. The subject should be instructed to periodically check the threads by feeling for the threads at the top of the vaginal canal and if, at any time of the study, a subject suspects that the Mirena may have been expelled, she should contact the investigator and the investigator should assess the need for an unscheduled visit to evaluate the location of the Mirena. The subject should be instructed to use non-hormonal back-up method of contraception until it is confirmed that the Mirena is in the proper location.

Subject is **in compliance** with Mirena when:

- Threads are visible, or,
- Threads are not visible (or not checked) but TVUS performed to localize the Mirena shows Mirena to be “In situ” or “Displaced intrauterine”.

Subject is **non-compliant** with Mirena when:

- Threads are not visible, and,
- TVUS performed to localize Mirena shows that the IUS is “Partially or totally expelled into vagina or cervical canal”, “Cervical perforation”, “Myometrial perforation”, “Localization in the peritoneal cavity”, or “Absent”.
- Threads are visible, but TVUS is performed for other reason(s) and Mirena localization is recorded as “Partially or totally expelled into vagina or cervical canal”, “Cervical perforation”, “Myometrial perforation”, “Localization in the peritoneal cavity”.

Non-compliance with Mirena necessitates discontinuation of the subject from the study. In case the IUS is partially expelled, it needs to be removed. In case perforation has occurred, the IUS needs to be removed using appropriate procedures.

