9.7.5 Back-up contraception

Subjects will be required to record the use of any back-up contraception (e.g. use of condoms for protection against sexually transmissible infections [STIs]) in their diaries. The only back-up contraception allowed during study treatment is the use of a barrier method (e.g. condoms).

Please see also Section 7.4.1

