A pregnancy will be allocated to the time period(s) that are relevant for the calculation of the PIs described above, e.g., a pregnancy that occurs on day 400 will be relevant for the 7th year PI, the two years PI (6th and 7th year), the three years PI (6th, 7th and 8th year), and the overall PI. Pregnancies that occur before Day 1 Year 6 of Mirena use will not count for the 1-year PI, 2-year PI and 3-year PI. Pregnancies that occur after the Mirena was removed or an expulsion was realized will not count for any PI.

It should be noted that e.g., pregnancies that occur after partial expulsion, but before Mirena removal will count for the PIs.

Furthermore, it should be noted that pregnancies that occur within 7 days after the end of exposure will count for the PIs.

Exposure times to be subtracted:

Subjects who apply additional concomitant contraception are not in risk or are under a lower risk of getting pregnant than subjects who do not apply additional contraception. In case a subject uses concomitant contraceptive methods (e.g., condoms to prevent STD); the respective 28-day reference period(s) of additional contraceptive method use will be excluded from the exposure time, unless a pregnancy occurred in that 28-day reference period.

Primary analysis

The primary method for the evaluation of the occurrence of pregnancy is the Pearl index defined as the number of pregnancies per 100 women years.

The PIs and the corresponding 2-sided 95 % confidence interval (CI) will be calculated using the model specified below.

Mathematical model for the calculation of the PI:

By assuming that the number of pregnancies follows a Poisson-distribution, the point estimate and the 95 % CI for the PI can be calculated as follows:

$$PI = x/E,$$

lower 95 % confidence limit of PI = $0.5 \times \chi^2_{(0.025, 2x)} / E$

upper 95 % confidence limit of PI = $0.5 \times \chi^2_{(0.975, 2(x+1))} / E$

where x = number of pregnancies,

E = exposure in 100 woman years (one woman year is 365 days of treatment exposure),

$\chi^2_{(\alpha, df)}$ is the alpha quantile from χ^2 -distribution with df degrees of freedom.

The primary analysis set will be the PAS Year 6 (for the analysis after 6 years), the PAS Year 7 (for the analysis after 7 years) and the PAS Year 8 (for the final analysis after 8 years), respectively. Furthermore, analyses will be repeated for the FAS.

Secondary analysis

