It should be noted that pregnancies that occur within 7 days after the end of exposure will count for the PI calculations.

Furthermore, it should be noted that pregnancies that occur after partial expulsion or first occurrence of non-compliance but before Mirena removal will count for the PI calculations.

Exposure times to be subtracted for Pearl index analyses:

Subjects who apply backup contraception are not at risk or are at lower risk of getting pregnant than subjects who do not apply backup contraception. In case a subject uses backup contraception (e.g., condoms to prevent sexually transmitted disease), the respective 28-day reference period(s) of backup contraception use will be excluded from the exposure time, unless a pregnancy occurred in that 28-day reference period. In the Pearl index analyses, the first 28-day reference period will start at Day 1 Year 6. Missing data will be considered as no use of backup contraception.

Primary analysis:

The primary method for the evaluation of the occurrence of pregnancy is the PI defined as the number of pregnancies per 100 woman-years.

The PIs and the corresponding 2-sided 95% confidence interval (CI) will be calculated using the model specified below.

Mathematical model for the calculation of the PI:

By assuming that the number of pregnancies follows a Poisson-distribution, the point estimate and the 95% CI for the PI can be calculated as follows:

$$PI = x/E,$$

$$\text{lower 95\% confidence limit of PI} = 0.5 \times \chi^2_{(0.025, 2x)} / E$$

$$\text{upper 95\% confidence limit of PI} = 0.5 \times \chi^2_{(0.975, 2(x+1))} / E$$

where x = number of pregnancies,

E = exposure in 100 woman-years,

$\chi^2_{(\alpha, df)}$ is the alpha-quantile from χ^2 -distribution with df degrees of freedom.

All PIs described above will also be presented by parity (no births vs. at least one birth), BMI (<30 kg/m² vs. ≥30 kg/m²) and age at insertion (<18 years vs. 18-25 years vs. 26-35 years, and <18 years vs. 18-35 years), age at baseline (18-25 years vs. 26-35 years vs. >35 years, and 18-35 years vs. >35 years), race and ethnicity. The age at insertion will be calculated as: age at baseline (recorded on the eCRF at baseline, Visit 2) minus 5 years.

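### Protocol 10.4: 200 completers and a 15% dropout rate without a time unit do not give 350 women, and 832 woman-years appears to be exposure before the back-up exclusion that the primary Pearl index applies

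*Protocol*

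**What the plan says.** Protocol Section 10.4 opens with "The sample size calculation is not based on statistical considerations". It then targets 200 women completing the eighth year and continues: "With an estimated dropout rate of 15%, the total number of women to be enrolled into the study treatment phase would be 350". Ten more women are added for the age restriction, making 360. Protocol Section 5 and SAP Section 3 repeat the pair: the target "is 360 women (200 women to complete study treatment").

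On exposure, Section 10.4 says: "This sample size will lead to an expected exposure (years 6 to 8 combined) of 832 women years (WY"). From this it gives four probabilities. The upper 95% limit for the years 6-8 PI stays at or below 1 with probability 76% at a true PI of 0.2 and 55% at 0.3. The distance from estimate to upper limit stays at or below 1 with probability >99.9% in both cases. The section ends in a redacted block.

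The PI denominator is defined elsewhere. Under Protocol Section 10.3.2.1 the 28-day reference periods of "additional contraceptive method use will be excluded from the exposure time, unless a pregnancy occurred in that 28-day reference period". SAP Section 6.2.1 has the same rule and adds: "Missing data will be considered as no use of backup contraception". Some back-up use is foreseen. Protocol Section 9.7.5 says "The only back-up contraception allowed during study treatment is the use of a barrier method (e.g. condoms"), and Section 9.6.3.8 says of a suspected expulsion: "The subject should be instructed to use non-hormonal back-up method of contraception until it is confirmed that the Mirena is in the proper location".

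**The concern.** There are two separate problems in one paragraph of Section 10.4.

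First, the 350 is presented as the consequence of 200 completers and 15% dropout, but neither plain reading of 15% produces it. A reader cannot tell which retention assumption underlies the study, or how many completers to expect.

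Second, the visible text deducts nothing from 832 woman-years for back-up contraception, although the primary analysis does. SAP Section 6.1.3.6 (extent of exposure) and the Kaplan-Meier analysis in SAP Section 6.2.1 leave back-up periods in, while the PI takes them out. If 832 is gross, the four probabilities describe an exposure other than the one in the PI. They are the only visible statement of what this sample size delivers for the primary variable.

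**Working it through.** **Inputs.** From Protocol 10.4: 200 completers, 15%, 350 women, 832 woman-years (WY), true PI 0.2 and 0.3. From Section 5: a 3-year treatment period. From Section 10.3.2.1: exact Poisson upper limit 0.5 × χ²(0.975, 2(x+1)) / E, with x pregnancies and E in 100 WY. The rationale in Section 15.1.1.2 confirms that 350 is the target for the final PI analysis set, with 360 covering the age restriction.

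**1. Women needed for 200 completers.**
- 15% in total: 200 / 0.85 = 235.3, so 236.
- 15% per year: 200 / 0.85³ = 325.7, so 326.
- 15 percentage points per year, added: 200 / 0.55 = 363.6, so 364.

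None gives 350. Going from 350 to 200 needs a loss of 1 − 200/350 = 42.9% in total, or 1 − (200/350)^(1/3) = 17.0% per year.

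**2. The 832 WY.**
- 350 women, 15% per year, losses at mid-year: 350 × 0.925 × (1 + 0.85 + 0.85²) = 832.8.
- Same, exponential loss: 350 × (1 − 0.85³) / (−ln 0.85) = 831.0.
- 350 women, 15% in total, linear: 350 × 3 × 0.925 = 971.
- 360 women, 15% per year, mid-year: 857.

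So 350 women at 15% per year reproduces 832 with nothing deducted. The same assumption gives 350 × 0.85³ = 214.9, about 215 completers.

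**3. The stated probabilities at E = 8.32.**
- Upper limit: the values 0.5 × χ²(0.975, 2(x+1)) for x = 2 and 3 are 7.225 and 8.767, so at most two pregnancies qualify. P(X ≤ 2) is 76.7% at mean 0.2 × 8.32 = 1.664, and 54.5% at mean 0.3 × 8.32 = 2.496. The plan states 76% and 55%.
- Precision: 0.5 × χ²(0.975, 2(x+1)) − x must not exceed E. At x = 9 it is 8.085, so x ≤ 9 qualifies, and the probability exceeds 99.9% at both PIs, as stated.

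**4. With back-up periods removed.** The documents give no share, so these shares are assumptions. One 28-day period per woman-year is 28/365 = 7.7%; two are 56/365 = 15.3%. Expected pregnancies are taken as PI × net exposure. Total exposure varies with dropout, so 350 women with exponential loss of 15% per year over 3 years were simulated (mean 831 WY, SD about 18 WY), and each simulated trial's limit used its own net exposure.

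| Share removed | Mean net WY, from 832 | Upper limit ≤ 1, PI 0.2 / 0.3 | Precision, PI 0.3 |
|---|---|---|---|
| none | 832 | about 77% / 55% | >99.9% |
| 7.7% | 832 × 0.923 = 768 | about 80% / 59-60% | about 99.8% |
| 12% | 832 × 0.88 = 732 | about 75% / 55% | about 99.3% |
| 15.3% | 832 × 0.847 = 704 | about 61% / 40% | about 98.6% |

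The upper-limit figures rise and then fall. At first, less exposure means fewer expected pregnancies while two still qualify. With more removed, a growing share of trials can afford only one.

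**The case against.** The strongest reply is that nothing depends on these figures. The size is openly non-statistical, no PI success criterion is stated, and the reported interval will be built on actual net exposure. The time unit can be recovered from the 832 WY, and the error in the head-count is a surplus: 350 women exceed the 326 needed. All of this stands, and it is why the point is minor.

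A second reply is that gross exposure is an inference. Fifteen percent in total gives 971 WY, and removing 14.3% for back-up use would also give 832 (971 × 0.857 = 832). The redacted block cannot be checked either. This is fair, and the second half of the point is therefore conditional. But that alternative implies 350 × 0.85 = 297.5 completers, far from 200, and the visible text states no such deduction. The yearly reading is the more natural one.

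A third reply is that the share removed may be small. Exclusion criterion 20 keeps out women at high risk for sexually transmitted disease, the back-up use in Section 9.6.3.8 lasts only until location is confirmed, and missing entries count as no use. This also stands, and no share is asserted here.

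A reader might infer that the stated probabilities are overstated, or that the study is too small. The documents do not support either: one removed period per woman-year would raise the upper-limit figures. A reader who treats exposure as one fixed number might also infer a sudden collapse at about 13% removed. That is an artefact of fixing exposure; with dropout varying, the decline is gradual.

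**Conclusion.** The point holds, at minor severity. The derivation of 350 does not reproduce from its own inputs: 236 or 326 women, not 350. The figures that do agree with each other are 350 women, 15% per year, 832 WY and 76%/55%. The 200 completers do not fit them, since about 215 would be expected.

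On that reading the four probabilities are for gross exposure and have not been shown for the exposure the PI uses. The size of the difference rests wholly on the assumed back-up share. It is small up to about 12% removed for the upper-limit figures, and about 15 points at two periods per woman-year (76% to 61%, 55% to 40%). The >99.9% at PI 0.3 no longer holds at one period, though only by about 0.1 point. The documents support neither a direction nor a shortfall in enrolment.

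**What to change.** Reword Section 10.4; leave enrolment, visits and analysis as they are.

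- Write 15% per year if that was meant, and give the expected completers from 350 women as about 215 with 200 as a minimum. If another input is the wrong one, correct that instead. With 200 as a minimum, the statements in Protocol Section 5 and SAP Section 3 can be read consistently.
- Label 832 WY as exposure before exclusion of back-up periods, if that is what it is.
- Restate the four probabilities for net exposure at a stated back-up share, for example none, one and two 28-day periods per woman-year, allowing for variation in exposure from dropout.

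The cost is a few sentences and a short calculation. Some restated probabilities would be higher than now and some lower. Protocol Section 13.1 requires investigator signatures and external approvals for any amendment, and SAP v5.0 was issued shortly before the Year 8 lock. The change does not justify an amendment of its own; it can go with another one or be noted as a clarification when the results are reported.
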